4.1.1 Dose Escalation

4.1.1.1 Dose-Escalation Decision Criteria

The decision to escalate to the next dose level and cohort will be made by the DDT following a review of all available safety and tolerability data, including AEs, ECGs, vital signs, and laboratory safety test results (i.e., hematology, clinical chemistry and urinalysis, etc.) collected at least 28 days postdose from a minimum of 6 participants (5 on active treatment and 1 on placebo) in Part 1, or a minimum of 5 participants on active treatment in Part 2, as well as available serum PK, PD, and ADA data up to 28 days postdose from a minimum of 5 participants on active treatment.

In addition, all available safety, tolerability, PK, PD, and ADA data from all previous dose level(s) will be reviewed. Dose escalation will only occur if the previous doses were tolerated and stopping rules were not met.

Dose-escalation steps will not exceed 5-fold increments.

4.1.1.2 Dose Decision Team

A DDT will review emerging study data and make recommendations regarding dose escalation and overall study conduct to ensure participant safety while receiving study treatment. The DDT will consist of the Investigators and the Sponsor members, collectively having expertise in clinical science, clinical pharmacology, pharmacodynamics, statistics, and clinical safety and will include at least one physician. Additional advisors may be consulted as deemed appropriate. The DDT will review emerging data that become available and will be empowered to pause, stop, or continue the study, or to continue it with modifications. Additional information about the DDT can be found in a separate Dose Escalation Plan (DEP).

4.1.1.3 Stopping Rules Criteria

4.1.1.3.1 Cohort Stopping Rules

Part 1

Dose escalation will be stopped and dosing at a given level will be stopped if one of the following circumstances occurs in participants treated with RO7565020 within the same dose cohort:

- Severe non-serious adverse reactions (Grade 3 or above, as per Division of AIDS [DAIDS] grading, v2.1, considered to be related to RO7565020) in 2 or more participants receiving RO7565020 in the same cohort, independent of the system organ classes.
- Any serious adverse reaction in 1 participant (i.e., a serious AE [SAE] considered to be related to RO7565020).
- Grade 2 or above clinically significant laboratory abnormalities, vital sign change, or ECG change, of the same type in 3 or more participants receiving RO7565020 in the same cohort.
- Other findings, which at the discretion of the DDT, indicate that dose escalation or dosing at that dose level should be stopped.
- Dose escalation will also be stopped if increasing the dose does not result in a significant increase in serum exposure of RO7565020.

Parts 2 and 3

Dose escalation and dosing at a given level of RO7565020 will be temporarily halted if one of the following circumstances occurs. Dosing might be resumed if deemed appropriate following the DDT review of the available safety, PK, and PD data. Relevant reporting and discussion with relevant DDT personnel and the Institutional Review Board (IRB)/ Independent Ethics Committee (IEC) will take place before potential resumption of dosing.

- Severe non-serious adverse reactions (Grade 3 or above, as per DAIDS grading, v2.1, considered to be related to RO7565020) in 2 or more participants receiving RO7565020 in the same cohort, independent of the system organ classes
- Any serious adverse reaction in 1 participant (an SAE considered to be related to RO7565020)
- Other findings which, at the discretion of the DDT members, indicate that dose escalation or dosing at that level should be stopped

In case dose escalation is stopped, lower doses within the tolerated dose range could be investigated or a dose repeated in subsequent cohorts to increase the amount of data within this tolerated dose range.

4.1.1.3.2 Individual Participant Stopping Rules

Infusion of RO7565020 will be stopped immediately (for an individual participant in the IV cohorts), and the participant will be discontinued from further treatment with RO7565020 (for an individual participant in the multiple-dosing cohorts), if the participant experiences any of the following:

- Severe non-serious adverse reactions (Grade 3 as per DAIDS grading, v2.1, considered to be related to RO7565020)
- Serious adverse drug reaction (i.e., an SAE considered to be related to RO7565020)
- Other findings which, at the discretion of the DDT members, indicate that dosing should be stopped

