6.7 TREATMENT AFTER THE END OF THE STUDY

Currently, the Sponsor does not intend to provide RO7565020 or NUC to participants after conclusion of the study or any earlier participant withdrawal.

The Sponsor will evaluate whether to continue to provide RO7565020 or NUC to participants after the main study is over, in accordance with the Roche Global Policy on Continued Access to Investigational Medicinal Product, available at the following website:

http://www.roche.com/policy_continued_access_to_investigational_medicines.pdf

7. **DISCONTINUATION OF STUDY, STUDY TREATMENT, AND PARTICIPANT DISCONTINUATION/WITHDRAWAL**

An excessive rate of participant withdrawals (either participants discontinuing study treatment or withdrawing from the study) can render the study non-interpretable. Therefore, unnecessary withdrawal of participants should be avoided and efforts should be taken to motivate participants to comply with all the study-specific procedures as outlined in this protocol.

Details on study and site closures are provided in [Appendix 1](#), Section 4.

7.1 **DISCONTINUATION OF STUDY TREATMENT**

Reasons for discontinuation of study treatment RO7565020 may include, but are not limited to, the following:

- Participant withdrawal of consent at any time.
- Any medical condition that the Investigator or Sponsor determines may jeopardize the participant's safety if he or she continues in the study.
- Investigator or Sponsor determination that treatment discontinuation is in the best interest of the participant.
- Pregnancy.
- Any other event that meets individual stopping criteria defined in Section [4.1.1.3.2](#).
- Safety and tolerability issues, e.g., acute reactions, not tolerable and not manageable with symptomatic treatment.

For Parts 2 and 3 only:

- Disease progression, e.g., any sign of development of liver cirrhosis (or liver imaging indicating cirrhosis), decompensation (e.g., ascites, variceal hemorrhage, Child-Pugh Class B or C clinical classification), or HCC
- Grade 4 ALT abnormal (i.e., $\geq 10 \times \text{ULN}$) as defined by the DAIDS Table for Grading the Severity of Adult and Pediatric Adverse Events (DAIDS AE grading table) confirmed within 48 to 72 hours
- Grade 3 ALT abnormal (i.e., $> 5 \times \text{to} < 10 \times \text{ULN}$) combined with total bilirubin $> 2 \times \text{ULN}$ (of which $> 35\%$ is direct bilirubin), or Grade 3 ALT abnormal and INR > 1.5

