2. DEFINITION OF SERIOUS ADVERSE EVENTS

If an event is not an AE per definition above, then it cannot be an SAE even if serious conditions are met (e.g., hospitalization for signs/symptoms of the disease under study, death due to progression of disease).

An SAE is defined as any untoward medical occurrence that at any dose:

- **Results in death.**
- **Is life-threatening.**

The term "life-threatening" in the definition of "serious" refers to an event during which the participant was at risk of death at the time of the event; it does not refer to an event which hypothetically might have caused death if it was more severe.

- **Requires inpatient hospitalization or prolongation of existing hospitalization** (see [Appendix 3](#)).

In general, hospitalization signifies that the participant has been detained (usually involving at least an overnight stay) at the hospital or emergency ward for observation and/or treatment that would not have been appropriate in the physician's office or outpatient setting. Complications that occur during hospitalization are AEs. If a complication prolongs hospitalization or fulfills any other serious criteria, the event is serious. When in doubt as to whether "hospitalization" occurred or was necessary, the AE should be considered serious.

- **Results in persistent or significant disability/incapacity**

Disability means substantial disruption of the participant's ability to conduct normal life functions.

This definition is not intended to include experiences of relatively minor medical significance such as uncomplicated headache, nausea, vomiting, diarrhea, influenza, and accidental trauma (e.g., sprained ankle) which may interfere with or prevent everyday life functions but do not constitute a substantial disruption.

- **Is a congenital anomaly/birth defect.**

- **Other significant events:**

Medical or scientific judgment should be exercised in deciding whether SAE reporting is appropriate in other situations such as important medical events that may not be immediately life-threatening or result in death or hospitalization but may jeopardize the participant or may require medical or surgical intervention to prevent one of the other outcomes listed in the above definition. These events should usually be considered serious.

Examples of such events include

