3.1. ASSESSMENT OF SEVERITY

The terms "severe" and "serious" are not synonymous. Severity refers to the intensity of an AE (rated as mild, moderate, severe, or according to a predefined grading criteria) (Division of AIDS Table for Grading the Severity of Adult and Pediatric Adverse Events [DAIDS]); the event itself may be of relatively minor medical significance (such as severe headache without any further findings).

Severity and seriousness need to be independently assessed for each AE recorded on the eCRF.

SAEs are required to be reported by the Investigator to the Sponsor immediately (i.e., no more than 24 hours after learning of the event).

The adverse event severity grading scale for the DAIDS (v2.1) will be used for assessing severity for adverse events. [Table 1](#) will be used for assessing severity for AEs that are not specifically listed in the DAIDS.

Table 1 DAIDS Adverse Event Severity Grading Scale for Events Not Specifically Listed in DAIDS Toxicity Grading Scale

| Grade | Description |
|-------|---|
| 1 | Mild symptoms causing no or minimal interference with usual social & functional activities with intervention not indicated |
| 2 | Moderate symptoms causing greater than minimal interference with usual social & functional activities with intervention indicated |
| 3 | Severe symptoms causing inability to perform usual social & functional activities with intervention or hospitalization indicated |
| 4 | Potentially life-threatening symptoms causing inability to perform basic self-care functions with intervention indicated to prevent permanent impairment, persistent disability, or death |
| 5 | Death |

Abbreviation: DAIDS = Division of AIDS

Note: Regardless of severity, some events may also meet seriousness criteria. Refer to definition of a serious adverse event (see above). DAIDS v2.1 grading scale is available at: <https://rsc.niaid.nih.gov/sites/default/files/daidsgradingcorrectedv21.pdf>. Developed by the DAIDS, National Institute of Allergy and Infectious Diseases, National Institutes of Health, U.S. Department of Health and Human Services.

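### The individual stopping rule names Grade 3 but omits *or above*, and for Part 3 the protocol does not say how Table 9 and Section 7.1 fit together for ALT at or above 10 × ULN

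*Combined protocol and SAP*

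**What the plan says.** Section 4.1.1.3.2 requires the infusion to be stopped (IV cohorts) or further dosing to be discontinued (multiple-dose cohorts) in three situations: "Severe non-serious adverse reactions (Grade 3 as per DAIDS grading, v2.1, considered to be related to RO7565020"); any related SAE; and "Other findings which, at the discretion of the DDT members, indicate that dosing should be stopped".

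The Part 1 cohort rule in Section 4.1.1.3.1 sets its threshold at "Grade 3 or above, as per Division of AIDS [DAIDS] grading, v2.1, considered to be related to RO7565020", and it must occur "in 2 or more participants receiving RO7565020 in the same cohort, independent of the system organ classes". The rule for Parts 2 and 3 has the same threshold and count. Part 1 also has a rule for "Grade 2 or above clinically significant laboratory abnormalities, vital sign change, or ECG change, of the same type in 3 or more participants".

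Appendix 2, Section 3.1 says: "Severity and seriousness need to be independently assessed for each AE recorded on the eCRF". For events outside the listed seriousness criteria, Appendix 2, Section 2 says: "Medical or scientific judgment should be exercised in deciding whether SAE reporting is appropriate in other situations".

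Section 7.1 gives reasons that may lead to discontinuation. Under "For Parts 2 and 3 only" it lists Grade 4 ALT (at least 10 × ULN) confirmed within 48 to 72 hours. It lists Grade 3 ALT only together with raised bilirubin or INR.

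Table 9 in Section 8.3.7 is offered as recommended guidance. With preserved hepatic function, ALT of 3–10 × ULN calls for weekly retesting. ALT above 10 × ULN calls for interruption in Part 3, twice-weekly retesting, and case-by-case consideration of re-introduction.

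**The concern.** In a first-in-human study the individual rule should name the most severe non-serious related reactions outright. Here it names Grade 3 and, on its literal wording, stops there. Section 2.3 counts pre-specified stopping criteria among the risk mitigations, and a decision left to discretion is not pre-specified.

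The ALT texts raise a related question. A Part 3 site working from Table 9 could consider re-dosing after a rise that Section 7.1, once confirmed, lists as a reason to discontinue. Table 9 points to neither Section 7.1 nor Section 4.1.1.3.2. Re-dosing is not quickly undone, because the antibody carries a half-life-extending mutation (Section 2.2.3).

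**Working it through.** The plan attaches no figure to this rule. Its only probability statement (Section 9.2) reproduces: 1 − 0.72⁵ = 80.65% for 5 participants and 1 − 0.76⁶ = 80.73% for 6. It does not bear on this point.

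**Step 1: one participant in Part 1b with a related Grade 4 laboratory value judged non-serious.**
- Individual rule, reaction bullet: names Grade 3, so not met literally.
- Individual rule, SAE bullet: not met, by assumption.
- Cohort rule, Grade 3 or above: needs at least 2 participants, so not met.
- Cohort rule, Grade 2 or above of the same type: needs at least 3 participants, so not met.
- Section 7.1 Grade 4 ALT entry: Parts 2 and 3 only, so not applicable.
- Section 7.1 reference to the individual criteria: leads back to Section 4.1.1.3.2.

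Specifically named stops met: 0. What remains is DDT discretion, the immediate sponsor contact for severe AEs (Section 4.1.1.4), and the general entries of Section 7.1. In Part 3 the result is the same for a Grade 4 value other than ALT; for ALT, the Section 7.1 entry applies once confirmed.

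**Step 2: ALT values in Part 3 with preserved hepatic function.**

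| ALT (× ULN) | Grade per 7.1 | Section 7.1, isolated ALT | Table 9 | Literal Grade 3 bullet, if related and non-serious |
|---|---|---|---|---|
| 5.1 or 9.9 | 3 | not listed | weekly retest; silent on dosing | met |
| 10 | 4 | listed if confirmed | weekly retest; silent on dosing | not met |
| 10.1 or 15 | 4 | listed if confirmed | interrupt; consider re-introduction | not met |

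The difference at exactly 10 is a single boundary value. The substantive one is above 10: a reason to discontinue in one place, possible re-introduction in the other, with no exception for a confirmed value.

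**Step 3: reach.** Planned active participants, from Sections 4.1 and 9.2:
- Part 1a: 6 cohorts × 6 = 36
- Part 1b (optional): 0 or 6
- Part 2: 5 × 6 = 30 to 7 × 6 = 42
- Part 3 (optional, at most 2 cohorts): 0 to 2 × 6 = 12

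The maximum total is 36 + 6 + 42 + 12 = 96. Multiple-dose reach is 0 to 6 + 12 = 18, at most 18/96 = 18.75%. The ALT point reaches 0 to 12, at most 12/96 = 12.5%. These count people dosed under the wording, not expected events.

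**The case against.** The strongest reply is that nobody obliged to stop for Grade 3 would continue for Grade 4. The cohort rules use the same phrase about severe non-serious reactions and gloss it twice as Grade 3 or above, so the omission is probably a slip. Many Grade 4 clinical events would be SAEs. Appendix 2 also adds that important events which may jeopardize the participant or need intervention should usually be considered serious. This stands, and it narrows the gap to an isolated laboratory value. It does not close it: life-threatening there means at risk of death at the time, and the listed liver example needs raised bilirubin or jaundice.

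On ALT, Section 7.1 is itself permissive, and Section 6.6.1 asks that interruption be considered before permanent discontinuation. The texts can therefore be read in sequence. That also stands, but the sequence is the reader's inference. Section 6.6.1 speaks equally of restarting when medically justified.

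Three stronger readings are tempting and not supported:
- **A retest delay at exactly 10 × ULN.** A reader might set the weekly retest (168 h) against the end of the confirmation window (72 h) and infer a 96 h delay. The Section 7.1 window applies whatever Table 9 says, Section 8.2.4 requires unexplained clinically significant values to be repeated immediately, and a Table 9 note allows the frequency to be adjusted.
- **Reach into the IV cohorts.** A reader might add 2 × 6 = 12 IV participants and claim 30 of 96. The Part 1a schedule shows no Day 1 chemistry, hematology or coagulation; the next samples are on Day 2, after the 2-hour infusion. A Grade 4 clinical event during infusion would mostly be an SAE and so already covered.
- **A conflict at Grade 3 ALT.** A reader might set the 3–10 × ULN row against the mandatory stop for related Grade 3 reactions. That row is silent on dosing, and silence does not contradict the stop.

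**Conclusion.** Both points hold as wording defects in a safety rule, at low severity. Section 4.1.1.3.2 lacks the *or above* of the cohort rules. Taken literally, it leaves a single related, non-serious Grade 4 event without a named individual stop. For Part 3, the documents do not say that confirmed Grade 4 ALT rules out the re-introduction Table 9 allows.

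The documents do not support saying that the protocol permits continued dosing after Grade 4 events, or that Section 7.1 and Table 9 flatly contradict each other: backstops exist, and both ALT texts are non-binding in form. The conclusion assumes that a Grade 4 laboratory value can be judged non-serious, which Appendix 2 allows. The counts assume planned cohort sizes, with no added or replacement participants, and fall to 0 if neither optional part runs. No hypothesis test, endpoint or estimate changes.

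**What to change.** 1. In Section 4.1.1.3.2, write Grade 3 *or above*, matching Section 4.1.1.3.1.
2. In Table 9, set the preserved-function bands to 3 to < 10 × ULN and ≥ 10 × ULN.
3. Add to the upper band: *repeat within 48 to 72 hours per Section 7.1; re-introduction may be considered only if Grade 4 ALT is not confirmed and no individual stopping rule in Section 4.1.1.3.2 is met.*
4. Leave the dosing text of the 3 to < 10 × ULN row unchanged. An instruction on isolated Grade 3 ALT there would be a dosing-policy decision that this point does not argue for.

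The cost is two words, two band limits and one sentence. The confirmation test is already in Section 7.1, so no scheduled visit is added and no retesting is removed. The change is best made before Part 1b or Part 3 opens.

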4.1.1.4 Communication Strategy

Information will be communicated, as follows:

- For all participants, during dose escalation in the study, the Investigator(s) must confirm to the Sponsor that the participant has been dosed and provide a brief summary of the status of the participant in terms of safety and tolerability to RO7565020, communicated by email and/or telephone.
- In the event of a severe AE or an SAE, the Investigator will contact the Sponsor immediately to discuss participant status and action taken/to be taken.
- After at least 28 days postdose from a minimum of 6 participants (5 on active treatment and 1 on placebo) in Part 1, or a minimum of 5 participants on active treatment in Part 2: The Sponsor will organize a teleconference with the Investigators to discuss the safety and tolerability of RO7565020 and to discuss the dose(s) for the next cohort. If the teleconference occurs prior to the end of the dose evaluation period, the Investigator will provide a final status prior to the start of the next cohort.

During each teleconference:

- AEs (see [Appendix 2](#)) will be discussed along with the results of PK data (if available), in addition to safety laboratory results and any other available data that may assist the dose escalation decision process.
- Dose escalation will only proceed to the next dose level if DDT are satisfied with the safety profile of the previous cohort and agree to move to the next dose level.
- If other RO7565020 dose levels are explored, it will be documented in writing, and both the Sponsor and Investigators will approve the minutes of these meetings to confirm agreement.

In addition to these communications, the Sponsor and Investigators will be in regular contact throughout the study, as per normal interactions during the conduct of a clinical study, and the Sponsor will arrange regular teleconferences and meetings to discuss study status.

4.2 SCIENTIFIC RATIONALE FOR STUDY DESIGN

The study rationale is provided in Section [2.1](#).

4.2.1 Rationale for Study Population

Part 1 will be conducted in healthy male participants, and female participants of non-childbearing potential or who agree to take contraceptive measures as required by the study, 18 to 65 years of age. The absence of potentially confounding diseases and co-medications (except for hormonal contraceptives for female participants) in healthy volunteers allows for a clearer and more consistent assessment of drug disposition, safety, tolerability, and ADA formation.

Parts 2 and 3 will be conducted in virologically suppressed participants with CHB, between 18 and 65 years of age, with preserved liver function and without significant fibrosis/cirrhosis. This population is considered optimal to evaluate the proof of mechanism of RO7565020 in humans as the first patient population. The virologically suppressed participants have a more stable disease phenotype compared to treatment-naïve patients who have elevated and fluctuating ALT levels, and the lower baseline HBsAg levels may increase the likelihood of attaining a treatment response. The study population is associated with a favorable benefit/risk profile and is considered appropriate for early phase clinical trials of novel CHB therapies within the current guidelines ([FDA 2022](#)).

As the participants enrolled in Parts 2a and 2b have different HBsAg levels at baseline, the proposed study will provide essential support for the selection of the RO7565020 multi-dose regimen for the future Phase II study in patients with CHB. Additionally, the safety, tolerability, and pharmacokinetics data, including the TMDD effect after single or multiple SC doses of RO7565020, will also provide essential information for supporting the future development of this target population.

4.2.2 Rationale for Control Group

In each cohort in Part 1a and in Part 1b, participants will be randomized (Sponsor-open, Investigator-blinded, and participant-blinded) at 6:2 to receive RO7565020 and placebo, respectively. This is considered sufficient to allow for unbiased comparisons of safety and tolerability of active treatment to placebo both within and across cohorts in absence of HBsAg.

It is considered unnecessary to include placebo controls in Parts 2 and 3, because placebo controls have negligible impact on HBsAg change over time, and the off-target safety profile at the same dose will have been assessed in healthy participants and the AEs in the presence of HBsAg would be most likely be of an immunological nature (e.g., as a consequence of HBsAg:HBsAb complex formation and possible tissue deposition) that can be easily attributed.

